### **11.5.3 Reporting Safety Observations by the Investigator to the IEC/IRB**

At each clinical site, the Principal Investigator is responsible for promptly notifying the relevant IEC/IRB of the following information, as applicable:

- All SAEs and subsequent follow-up information.
- Any SAE reports and follow-up reports received from the sponsor or the sponsor's designee.

### **11.5.4 Other Reportable Information: Pregnancy**

In the event that a patient is confirmed to be pregnant during the study or during follow-up, the investigational product must be discontinued immediately and permanently.

Any pregnancy or fathering of a child, which occurs up to 30 days within the last application of study medication should immediately be reported. The investigator will be asked to complete a pregnancy report provided by the sponsor. In addition, the investigator should provide follow-up information regarding the course of the pregnancy, including perinatal and neonatal outcome.

## **12 STATISTICAL ANALYSIS**

### **12.1 Statistical Methods**

The primary efficacy analysis will be conducted once all patients have completed (or withdrawn prior to Visit 10) at Week 24±3 days (End of the Efficacy Phase). The primary efficacy analysis will include the key primary/secondary efficacy data, all safety data available up to the data cut-off date of the last patient reaching Week 24±3 days, and PK parameter analysis. The reporting of Week 24±3 days data will allow for an early submission of an application for regulatory approval of Lojuxta® in the paediatric indication. The final statistical analysis will be performed when all patients have completed the Follow-up Visit (Visit 23) at Week 108±7 days. Efficacy, safety, and exploratory data collected during both the Safety Phase and follow-up will be included.

No interim efficacy analyses for efficacy and/or futility will be performed as outlined in Section 12.3.3 *Interim Analysis*.

#### **12.1.1 Tests of Hypotheses and Significance Levels**

The primary and secondary efficacy parameters collected during the Efficacy Phase of the study will be statistically tested using a 2-sided test at the 5% significance level.

To address the efficacy objectives, the efficacy parameters will be tested sequentially in a step-wise fashion, thereby controlling the overall type I error. First, the primary testing for percent change from Baseline in LDL-C at Week 24±3 days will be performed. If this test is statistically significant with a 2-sided  $\alpha = 0.05$  and is statistically significant in a positive

direction, then the tests of the secondary hypotheses will be performed in the following specified order at Week 24±3 days:

1. Non-HDL-C
2. TC
3. VLDL-C
4. apo B
5. TG
6. Lp(a)

If at any step of the testing procedure a non-significant p-value is reached, further tests in the sequence will be performed and p-values will be reported as a measure of the strength of effect without declaring statistical significance.

Analysis of other secondary endpoints collected during the Efficacy Phase and of endpoints collected during the Safety Phase will be analysed without adjustment for multiplicity.

### **12.1.2 Determination of Sample Size**

At least 30 evaluable patients (≥8 patients in each of the following age groups, determined by age at Baseline: 5 to 10 years, 11 to 15 years, and 16 to ≤17 years) are required at Week 24±3 days to provide 92% power, assuming a 25% reduction from Baseline in LDL-C with a standard deviation (SD) of 40% and a 2-sided  $\alpha$  of 0.05. To allow for up to 33% dropout during the Efficacy Phase (prior to Week 24±3 days), an additional 15 patients will be enrolled, resulting in a total sample size of approximately 45 patients. Enrolment will be stratified to ensure approximately equal numbers of patients in the following age groups: 5 to 10 years, 11 to 15 years, and 16 to ≤17 years.

As a conservative assumption, the estimated 25% mean reduction represents approximately 60% of the 41% mean reduction from Baseline to Week 26/End of Efficacy Phase seen in the adult study UP1002/733-005, Intent-to-Treat (ITT) Population. This is the same assumption that was used for the sample size in the adult study. The SD represents an approximate 1/3 increase from the 31% SD observed in the adult study. This increase in SD was used to account for potentially increased variability across the 3 age groups.

## **12.2 Definition of Study Populations**

The statistical analysis will be based on the following study populations:

- The safety analysis set (SAF) will include all patients treated with at least 1 dose of study medication. The SAF will be used for all safety analyses.
- The full analysis set (FAS) will include all patients in the SAF who receive at least 1 dose of study medication and who have a Baseline and at least 1 post-Baseline measurement of LDL-C. The FAS will be used for all efficacy analyses.
- All patients from the FAS will be assigned to a completer analysis set (CAS), if they have not discontinued the study during the Efficacy Phase (up to Week 24) irrespective of the reason for discontinuation. The CAS will be used for all efficacy analyses during the Efficacy Phase.
- Patients who reasonably adhered to all protocol conditions i.e., who have met the eligibility criteria and will have received planned study medication without important protocol deviations considered to have a serious impact on the efficacy results with the Efficacy Phase of the study, will constitute the per-protocol analysis set (PP). The PP will be used for supplementary efficacy analyses during the Efficacy Phase.

The data obtained will be used to check whether the study protocol was adhered to (e.g., inclusion and exclusion criteria, time windows, concomitant medication). Case-by-case decisions regarding exclusions of patients from the PP analysis will be made in a data review meeting.

Patients who are not treated will not be assigned to any of these analysis sets. All participants who pass Screening and enter the run-in period, irrespective of whether they received study medication, will be included in the Enrolled Set.

The FAS will serve as the primary population for the analysis of efficacy data in this study. Specifically, the primary, confirmatory endpoint analysis will be done using the FAS. In addition, efficacy analyses will be done using the PP and the CAS, serving as sensitivity analyses. Safety analyses will be conducted using the SAF.

## **12.3 Planned Analysis**

Full details of the planned analyses will be documented in a Statistical Analysis Plan prior to database lock. The primary estimand will be a 'treatment policy' estimand which will be defined in the Statistical Analysis Plan.

### **12.3.1 Disposition and Exposure**

Patient disposition, medical history, prior and concomitant medication use including current LLT and LA, and study medication exposure will be summarised.

### **12.3.2 Demographic Data and other Baseline Characteristics**

Demographics and other Baseline characteristics will be summarised in total and by age group by means of summary statistics (number of patients, mean, standard deviation, minimum, median, maximum) for continuous variables and by absolute and relative frequencies for categorical variables. Baseline characteristics are defined as all results of the examinations performed prior to the first administration of study medication.

Relevant demographic and Baseline characteristics will be summarised using descriptive statistics. These variables include:

- Demographic variables: Age, gender, race, and ethnicity
- Baseline:
  - Height, weight, BMI, and BSA
  - LDL-C, TC, Non-HDL-C, VLDL-C, Lp(a), TG, and apo B
  - Disease characteristics

### **12.3.3 Interim Analysis**

No interim efficacy analyses for efficacy and/or futility will be performed.

The primary efficacy analysis and final statistical analysis will be performed as described in Section 12.1 *Statistical Methods*.

An independent DSMB will periodically review the safety data as described in Section 4.3 *Data Safety Monitoring Board*.

### **12.3.4 Planned Analysis for Primary Endpoint**

The primary efficacy endpoint, percent change from Baseline in directly measured LDL-C at Week 24±3 days, will be analysed using the one-sample t-test to test the null hypothesis that the percentage change from Baseline is equal to zero against the alternative hypothesis the percentage change from Baseline is not equal to zero. The percentage change at

Week 24±3 days, together with the corresponding 2-sided 95% confidence interval and p-value will be presented. Missing data will be imputed using last observation carried forward (LOCF). The analysis will be based on the FAS Population.

A sensitivity analysis will be performed using a Mixed Model Repeated Measures (MMRM) model with the missing at random assumption (i.e., missing data will not be imputed using LOCF or any other method). The analysis will be based on the FAS Population.

Supplementary analyses will include the one-sample t-test and summaries based on the PP and CAS.

Sub-group analyses will be conducted using an Analysis of Covariance (ANCOVA) model to estimate the mean percentage change and 2-sided 95% confidence intervals within each sub-group at Week 24±3 days. Sub-group analyses will be performed for the 3 age groups and also based on documented CVD history, established CVD history, concomitant LLT medication, and dose reduction of study medication. These analyses will be based on the FAS Population.

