## 7.2 Treatment Schedule

After stabilisation of the patient on his/her current MTD of LLT (including LA when applicable) during the 6-week Run-in Period, treatment with lomitapide will be started as add-on therapy on D0 of the Efficacy Phase.

Lomitapide capsules will be provided in 4 dose strengths of 2 mg, 5 mg, 10 mg, and 20 mg. Dosing will be initiated at the recommended starting dose and escalated to the maximum dose as applicable to the age groups (see Table 2 and Figure 3) based upon safety and tolerability in addition to LDL-C values.

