### **12.3.5 Planned Analysis for Secondary Endpoints**

The secondary lipid parameter endpoints will be analysed as described for the primary endpoint in Section 12.3.4 *Planned Analysis for Primary Endpoint*.

As secondary analyses of the pattern of LDL-C and lipid parameter change over time, a MMRM model will be used, including all available data (all visits from Baseline through Week 104±1 week). Observed changes and percent changes from Baseline at each timepoint will be summarised.

Number and percentage of patients treated with standard LLT (including LA when applicable) will be summarised overall and by age group. Any dose increases of standard LLT/increased frequency of LA will be summarised.

Number and percentage of patients with LDL-C falling below the target level will be summarised by study visit at any time up to Week 24±3 days and at any time up to Week 104 by age group and overall.

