### **12.5 Handling of Missing Data**

Care will be taken during the conduct of this study to minimise the amount of missing data. The FAS will be used for the primary analysis of all efficacy endpoints. Each patient in the FAS will have a Baseline value and at least one post-Baseline value. Because this is a single-arm study, for patients who have missing data at the time point of interest, the LOCF approach will be used in all Efficacy Phase analyses. However, for the fasting lipid panel, it is not appropriate to carry forward Screening/run-in period values if a Baseline value is missing as this value would be obtained prior to stabilisation of the patient on LLT so LOCF will not be used for these analyses.

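### Does the primary one-sample t-test lose anything that matters by leaving out the age groups used to stratify enrolment?

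*Protocol*

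**What the plan says.** Section 12.1.2 states that "Enrolment will be stratified to ensure approximately equal numbers of patients in the following age groups": 5 to 10, 11 to 15 and 16 to 17 years, with at least 8 evaluable patients in each, classified by age at Baseline. It plans on a 25% reduction with an SD of 40%, raised from the 31% seen in the adult study, and explains: "This increase in SD was used to account for potentially increased variability across the 3 age groups".

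For the analysis, Section 12.3.4 says that the primary endpoint "will be analysed using the one-sample t-test to test the null hypothesis that the percentage change from Baseline is equal to zero", reported with a two-sided 95% confidence interval in the FAS. Section 12.3.5 extends this to the other lipids: "The secondary lipid parameter endpoints will be analysed as described for the primary endpoint in Section 12.3.4". Age enters the LDL-C analysis as a subgroup factor in an ANCOVA: "Sub-group analyses will be performed for the 3 age groups". The terms of the sensitivity MMRM are not listed, and Section 12.3 leaves full analysis details to the SAP.

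**The concern.** It is usual to carry a design stratum into the analysis. When stratum sizes are set by design, differences between stratum means add nothing to the sampling variation of the overall mean. A one-sample t-test nevertheless leaves them in its SD, so its interval is wider than the design requires.

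There are hints that the age groups could differ. Doses differ by group (Section 7.2: "Dosing will be initiated at the recommended starting dose and escalated to the maximum dose as applicable to the age groups"), and the sponsor inflated the SD with the age groups in mind. In a rare disease with a target of 30 evaluable patients, unnecessary width in the main estimate and in six secondary lipids would be worth avoiding, especially if wording and two degrees of freedom were the only price.

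**Working it through.** **The plan's own figures.** Inputs from Section 12.1.2: n = 30, reduction 25, SD 40, two-sided 5%.
- Noncentrality: 25/40 × √30 = 3.42. Power is 91.1% by the exact noncentral t (29 df) and 92.8% by the normal approximation. The stated 92% lies between them.
- Dropout: 30/(1 − 0.33) = 44.8, so 45 enrolled.

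The sample size is adequate for the test that is planned.

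**What an age-group term could save.** Let s be the within-group SD and d the gap between neighbouring group means, with equal groups. The lowest-to-highest difference is then 2d.
- Expected total variance seen by the t-test: s² + 2(n/3)d²/(n − 1).
- t-test half-width: t(n − 1) × total SD/√n.
- Age-group model half-width: t(n − 3) × s/√n.

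Example with n = 30, s = 40, d = 10: variance 1600 + 2000/29 = 1669, SD 40.85. The t-test gives 2.045 × 40.85/5.477 = 15.25 and the model gives 2.052 × 40/5.477 = 14.98.

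The protocol gives no age-group means, so every d below is an assumption.

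| s | d | lowest to highest | t-test | model | t-test wider by |
|---|---|---|---|---|---|
| 40 | 0 | 0 | 14.94 | 14.98 | −0.3% |
| 40 | 5 | 10 | 15.02 | 14.98 | 0.2% |
| 40 | 10 | 20 | 15.25 | 14.98 | 1.8% |
| 40 | 20 | 40 | 16.17 | 14.98 | 7.9% |
| 31 | 5 | 10 | 11.68 | 11.61 | 0.6% |
| 31 | 10 | 20 | 11.98 | 11.61 | 3.2% |
| 31 | 20 | 40 | 13.13 | 11.61 | 13.1% |

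**How plausible are the large gaps?** Around the planned mean of 25%, d = 20 means group reductions of about 5%, 25% and 45%. Section 2.5 derives the doses by age on the assumption that response and concentration-response are similar in children and adults. Section 7.3.1 stops escalation below an LDL-C threshold, which tends to narrow differences between groups. Doses chosen by age in this way are weak evidence that response will differ by age.

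**Effect on the test.** At n = 30 and s = 40, power is 90.4% for the t-test against 90.9% for the model at d = 10, and 88.0% against 90.9% at d = 20. The number analysed should usually be nearer 45 than 30. The FAS takes treated patients "who have a Baseline and at least 1 post-Baseline measurement of LDL-C", and Section 12.5 adds that "for patients who have missing data at the time point of interest, the LOCF approach will be used in all Efficacy Phase analyses". At n = 45 and SD 40 the exact power is 98.4%.

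**What the age-group model would risk.** Its narrower interval is correct only for a fixed age mix. Section 12.1.2 promises approximate equality and a minimum of 8 per group, which is 3 × 8 = 24 patients. That leaves 6 of 30, or 21 of 45, not fixed by the minimum. Simulated coverage of the equal-mix mean:
- Fixed 10/10/10, d = 20: t-test 96.5% (s = 40) and 97.3% (s = 31); model about 95%.
- 8 per group fixed and the rest at random, d = 20: t-test 95.4% to 96.9%; model 93.6% to 94.7%.
- Fully random mix, n = 30, d = 20: t-test 95.1%; model 93.2% (s = 40) and 91.9% (s = 31).

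In these runs the t-test never falls materially below 95%, whereas the model can.

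**The case for a change.** The best case for change is that the sponsor raised age heterogeneity itself and then chose an analysis that cannot remove it. If the whole rise in SD from 31% to 40% came from differences between group means, the neighbouring gap would be about 30 points, more than the gaps tabulated. The remedy looks cheap: weight the groups by their observed share, so the estimate equals the plain mean and only the standard error and degrees of freedom change.

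Much of this is correct. The primary test has no age term, the direction of the effect is right, and the gains calculate as claimed under their assumptions. Three things weaken it.

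- A 30-point gap around a mean reduction of 25% implies group results of a 5% increase, a 25% reduction and a 55% reduction. The SD wording can as well mean greater spread within groups. Either way, the inflated SD means the planned power already allows for it.
- The remedy ties the interval to the observed age mix, which is only partly controlled. Stratified enrolment takes place at Visit 2, at least 6 weeks before Baseline (Section 9.3.1), whereas the groups are defined by age at Baseline, so a child may change group in between.
- Unequal within-group SDs favour the t-test. With groups of 8/8/14 and SDs of 50/50/25, the model covers about 94.3% to 94.6% and the t-test 95.1% to 95.4%.

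**Conclusion.** The concern does not hold. Nothing in Sections 12.1.2, 12.3.4 or 12.3.5 is misstated or contradictory on this point, and the choice of test is sound. The one-sample t-test gives a valid, if anything slightly cautious, interval, and it does not need the age mix to be fixed.

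At n = 30 and SD 40, the width forgone is 0.2% to 1.8% if the age-group means span 10 to 20 points, and nothing if they are equal. It approaches 8% (13% at SD 31) only if the means span 40 points, which the protocol does not suggest. These sizes rest on assumed gaps, equal group sizes and a common within-group SD. In return, the model would give up some protection of coverage in a small single-arm trial. Statisticians may reasonably prefer either analysis. Age-group estimates with intervals are already planned as subgroup analyses, and any further use of age group can be settled in the SAP.

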### **12.3.5 Planned Analysis for Secondary Endpoints**

The secondary lipid parameter endpoints will be analysed as described for the primary endpoint in Section 12.3.4 *Planned Analysis for Primary Endpoint*.

As secondary analyses of the pattern of LDL-C and lipid parameter change over time, a MMRM model will be used, including all available data (all visits from Baseline through Week 104±1 week). Observed changes and percent changes from Baseline at each timepoint will be summarised.

Number and percentage of patients treated with standard LLT (including LA when applicable) will be summarised overall and by age group. Any dose increases of standard LLT/increased frequency of LA will be summarised.

Number and percentage of patients with LDL-C falling below the target level will be summarised by study visit at any time up to Week 24±3 days and at any time up to Week 104 by age group and overall.

### **12.3.6 Planned Analysis for Safety Endpoints**

Safety will be assessed using the SAF Population, including all patients who receive any amount of study medication, and will be based on evaluation of AEs, laboratory data, vital signs and physical examination findings, height, weight, BSA and BMI, ECG, echocardiography (if available) and hepatic fat. Safety data summary statistics will be presented overall and by age group.

Adverse events will be coded using the Medical Dictionary for Regulatory Activities (MedDRA) for purposes of summarisation. All AEs occurring during the study will be included in by-patient data listings and will be summarised overall and by age group. Events leading to death, SAEs, and events resulting in study discontinuation will be summarised. Adverse events of special interest, such as hepatobiliary AEs and hepatotoxicity of different levels, will be summarised (see Section 11.1.6 *Adverse Events of Special Interest*).

Reported clinical laboratory results and changes from Baseline will be summarised using descriptive statistics overall and by age group. Shift tables and summaries of potentially clinically significant findings will be presented. Reported values and changes from Baseline for vital signs, ECG findings, and echocardiography (if available) will be summarised by time point overall and by age group. For lipid accumulation in the liver, the number and percentage of patients with liver fat content ≤10%, >10% and ≤20%, and >20% will be summarised overall and by age group. Changes from Baseline over time will be presented in shift tables for ECG results, echocardiography (if available) and lipid accumulation in the liver.

To assess sexual maturation, changes from Baseline in Tanner staging results will be presented in shift tables and graphically.

#### **12.3.7 *Planned Analysis for Exploratory Endpoints***

The percentage change from Baseline in mean CIMT and mean FMD at Week 56±3 days and at Week 104±1 week will be assessed overall and by age group.

The number and percentage of patients with (tendon/cutaneous) xanthomas present, and locations, will be summarised overall and by age group at Baseline, Week 56±3 days and Week 104±1 week. The number and percentage of patients with resolution and regression of pre-existing xanthoma (Baseline) to Week 56±3 days and Week 104±1 week will be summarised overall and by age group.

Changes from Baseline in parameters assessed by the Liposcale® Test will be summarised at Week 4±3 days, Week 8±3 days, Week 12±3 days, Week 16±3 days, Week 20±3 days and at Week 24±3 days.

#### **12.3.8 *Planned Analysis for Palatability Endpoints***

The number and percentage of patients responding to each question regarding palatability will be presented over time overall and by age group.

#### **12.3.9 *Planned Analysis for Pharmacokinetic Endpoint***

PK data will be used in population PK/PD modelling for the lomitapide program. This will be described in a separate document.

### **12.4 Statistical Criteria for Study Termination**

No interim analysis for futility will be performed. Therefore, no criteria for early termination of the study from a statistical perspective are considered.

### **12.5 Handling of Missing Data**

Care will be taken during the conduct of this study to minimise the amount of missing data. The FAS will be used for the primary analysis of all efficacy endpoints. Each patient in the FAS will have a Baseline value and at least one post-Baseline value. Because this is a single-arm study, for patients who have missing data at the time point of interest, the LOCF approach will be used in all Efficacy Phase analyses. However, for the fasting lipid panel, it is not appropriate to carry forward Screening/run-in period values if a Baseline value is missing as this value would be obtained prior to stabilisation of the patient on LLT so LOCF will not be used for these analyses.

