#### 4.1.2 *Secondary Endpoints*

- Percent change from Baseline at Week 24±3 days for the following lipid parameters: TC, Non-HDL-C, VLDL-C, TG, Lp(a), and apo B.
- Percent change from Baseline at all other time points through Week 104±1 week for the following lipid parameters: LDL-C, TC, Non-HDL-C, VLDL-C, TG, Lp(a), and apo B.
- Total number and percent of patients with a change from Baseline in LLT and LA from Week 24±3 days through Week 104±1 week.
- Total number and percent of patients achieving the EAS recommended target LDL-C of <135 mg/dL (3.5 mmol/L) in paediatric HoFH patients at Week 24±3 days and at any time on study.

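### LOCF as written counts a child who left before Week 24 with a last LDL-C below 135 mg/dL as at the EAS target at Week 24

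*Protocol*

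**What the plan says.** The endpoint in Protocol Section 4.1.2 is "Total number and percent of patients achieving the EAS recommended target LDL-C of <135 mg/dL (3.5 mmol/L) in paediatric HoFH patients at Week 24±3 days", with a second part covering attainment at any time on study. Section 12.3.5 describes the analysis: "Number and percentage of patients with LDL-C falling below the target level will be summarised by study visit at any time up to Week 24±3". A second summary runs to Week 104, and results are split by age group as well as shown for all patients. The section sets no missing-data rule for this summary.

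The general rule is in Section 12.5: "for patients who have missing data at the time point of interest, the LOCF approach will be used in all Efficacy Phase analyses". The same section says "The FAS will be used for the primary analysis of all efficacy endpoints". Under Section 12.2 the FAS holds treated patients "who have a Baseline and at least 1 post-Baseline measurement of LDL-C", so a child who withdraws after one post-Baseline lipid panel stays in it. The completer set (CAS) keeps FAS patients only "if they have not discontinued the study during the Efficacy Phase (up to Week 24) irrespective of the reason for discontinuation".

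Section 12.5 states one limit on LOCF for the fasting lipid panel: "it is not appropriate to carry forward Screening/run-in period values if a Baseline value is missing". The sentence ends by saying that LOCF is not used for those analyses.

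Section 12.1.2 sets the planned dropout: "To allow for up to 33% dropout during the Efficacy Phase", which takes 30 evaluable patients to about 45 enrolled.

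**The concern.** For a mean percent change, LOCF is a debatable imputation. For a count of patients at target on a named date it makes a factual claim about each child. A child who leaves for an adverse event around Week 14 with a last LDL-C of 128 mg/dL would be listed as at target at Week 24, about ten weeks later, with no measurement then.

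Two features of the protocol make this awkward. First, Section 12.3 names a treatment-policy approach for the primary estimand. A value taken at or before withdrawal does not describe a child's status at Week 24 after leaving. Second, the endpoint has two deliberately different parts. A real earlier value below 135 mg/dL already earns credit under the any-time part, and LOCF moves the same value into the Week 24 part.

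The trial has no comparator, and Section 12.1 says the Week 24 report is meant to support an early regulatory application. The share of children at target is one of the results a clinical reader will take from it.

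**Working it through.** **1. The plan's own figures.** Inputs from Section 12.1.2: n = 30, mean reduction 25%, SD 40%, two-sided 0.05, dropout up to 33%. The standardised effect is 25/40 = 0.625. A one-sample t-test at n = 30 gives 91.1% power, and the normal approximation gives 92.8%. The stated 92% is reproduced to within about one point. For dropout, 30/0.67 = 44.8, so 45 enrolled and 15 leavers at the maximum.

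**2. Does the rule reach this endpoint?** The Week 24 target count is an Efficacy Phase efficacy analysis on the FAS, and Section 12.3.5 makes no exception for it. The closing words of Section 12.5 might be read as removing LOCF from every lipid analysis. That reading contradicts Section 12.3.4, which imputes the primary lipid endpoint by LOCF. The words make sense only for a missing Baseline value. The rule therefore applies.

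**3. Formula.** Let N be the FAS size, d the leavers without a Week 24 value, p the target rate among the N − d completers, and q the share of leavers whose last value is below 135 mg/dL.

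- LOCF rate = [(N − d)p + dq]/N
- Leavers counted as not at target = (N − d)p/N
- Excess of LOCF over that count = dq/N
- LOCF minus completers-only rate = d(q − p)/N

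N = 45 assumes that every leaver has at least one post-Baseline LDL-C. Children who leave before one are outside the FAS under every rule. The protocol gives neither p nor q, so both are assumptions.

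**4. Excess over counting leavers as not at target, N = 45.**

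| Leavers d | q = 0 | q = 0.10 | q = 0.20 |
|---|---|---|---|
| 15 (maximum planned) | 0 | 15 × 0.10/45 = 3.3 points | 15 × 0.20/45 = 6.7 points |
| 9 | 0 | 9 × 0.10/45 = 2.0 points | 9 × 0.20/45 = 4.0 points |
| 6 | 0 | 6 × 0.10/45 = 1.3 points | 6 × 0.20/45 = 2.7 points |

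Each such child adds 1/45 = 2.2 points. For reference, Section 2.4.2 reports that 23 of 29 adults completed the Efficacy Phase of the pivotal study, a loss of 6/29 = 21%. That is close to the row with 9 of 45 (20%).

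**5. Worked example, d = 15 and p = 0.40 (assumed).** Completers at target: 30 × 0.40 = 12.

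- Leavers counted as not at target: 12/45 = 26.7%
- LOCF, q = 0.10: (12 + 1.5)/45 = 30.0%
- LOCF, q = 0.20: (12 + 3)/45 = 33.3%
- Completers only: 12/30 = 40.0%

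With q = 0.20, LOCF is 6.7 points above the first figure and 6.7 points below the last: 15 × (0.20 − 0.40)/45 = −0.067.

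**The case against.** A reader might infer that LOCF always inflates attainment, or that the number of children wrongly counted can be stated. The documents support neither. The excess cannot be negative when the comparison is with counting leavers as failures, but that follows from the definition, because any other handling of leavers adds to that count. It is itself a convention, not an observed truth. Against completers only, LOCF is lower whenever q is below p. A fixed size would need the onset of effect, the timing of withdrawal and the response of leavers, none of which the protocol gives. Doses are titrated up to Week 16 or 20, so early leavers will have had lower doses and q may be small.

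Further points on the other side:

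- **The carried value may not be on drug.** Sections 7.4 and 9.7 require the End of Treatment assessments at premature discontinuation, including a fasting lipid panel. The last observation may be that sample, and the protocol does not say which value is carried. This stands. It affects q, but the sample is still not a Week 24 value unless it falls in that window.
- **A contrasting analysis is planned.** Section 12.2 provides for CAS analyses. This stands in part: the CAS drops leavers and does not count them as failures, so it does not correct the FAS percentage.
- **The endpoint is descriptive.** It lies outside the six-step sequence in Section 12.1.1. This stands. No test, type I error or power figure depends on it. The sampling error is also larger than the shift: at 26.7% of 45 the 95% half-width is 1.96 × √(0.267 × 0.733/45) = 12.9 points. But the shift is a systematic difference that one sentence removes.
- **The SAP may settle it.** Section 12.3 defers full details to the SAP, which was not available here. This does not answer the point, because Section 12.5 states a rule for all Efficacy Phase analyses and leaves no gap to fill.
- **A blanket missing-equals-failure rule is too blunt.** It would also fail a child still on drug whose sample was lost. This stands, and the fix separates the two cases.

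**Conclusion.** The point holds in a limited form. As written, the protocol reports a child who discontinued before Week 24 with a last LDL-C below 135 mg/dL as at target at Week 24 without a Week 24 measurement. Relative to counting such children as non-achievers, the excess is dq/N: between 0 and 6.7 points for q from 0 to 0.20 at the maximum 33% dropout, and proportionally less at lower dropout. This rests on an assumed q and on all 45 patients being in the FAS.

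Only the Week 24 part of the endpoint is affected. The claim that leavers would really be above target at Week 24 is plausible but also an assumption. Section 5.1 requires entry LDL-C above 160 mg/dL, or above 130 mg/dL with established CVD, on background therapy, so a return to entry level would put nearly all of them above 135 mg/dL. The protocol schedules no Week 24 measurement after withdrawal that would show it. The change should be made, but nothing in the confirmatory analysis depends on it.

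**What to change.** In Section 12.3.5, with a cross-reference in Section 12.5, state for the Week 24 EAS-target endpoint with the FAS as denominator:

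1. Any observed Week 24 LDL-C is used.
2. A patient who discontinued before Week 24 and has no Week 24 value counts as not having achieved the target.
3. A patient still on study whose Week 24 sample was only missed or lost follows one stated rule: counted as not achieved, with LOCF as a sensitivity analysis.
4. The full LOCF count is shown as a supplementary line.

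Reword the last sentence of Section 12.5 so that its exclusion of LOCF refers only to missing Baseline lipid values and cannot be read against Section 12.3.4.

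The cost is about a sentence of text and a slightly less favourable reported percentage. No new data, visits or patients are needed.
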